### Protocol

The proposed study is a pragmatic randomized controlled pilot trial of neonatal warming techniques with participants allocated in a 1:1 ratio using a random block allocation table using blocks of size 4 and 6 that are stratified by gestational age ranges of 35-36 weeks and 6 days and 32-34 weeks and 6 days. Since there cannot be a placebo intervention, neither the patient nor the neonatal team will be blinded to the group assignment. The group assignments will be made and coded by a third party at the time of randomization. Patients will be randomized to their respective groups immediately prior to surgery.

We will aim for an operating room temperature of 65-70 degrees F. The surgical technician will be provided with the necessary neonatal wraps and mattresses in a sterile fashion, and they will ensure these are available on the surgical field once the cesarean has begun. In the intervention group, the thermal mattress will be activated immediately prior to hysterotomy and placed on the sterile field with delivery of the infant directly onto the mattress. The infant will be dried, stimulated and bulb suctioned as deemed necessary per standard of care followed by wrapping. In the non- intervention group, the infant will be delivered onto the sterile field, dried and suctioned as deemed necessary per OU standard. Cord clamping will be delayed for 60 seconds in all infants under the supervision of both the obstetrician and the neonatal resuscitation team. If either team believes delayed cord clamping is no longer considered safe, as is our usual protocol, the cord will be clamped and cut and the baby will be handed off to the neonatology team. After the infant is handed to the neonatology team along with all group assignment specific materials (wrap and thermal mattress, if in the intervention group), neonatal temperature will be assessed immediately upon arrival to the resuscitation warmer using a digital thermometer placed in the axillary space. Infant temperature will be recorded at 1) arrival to the warmer, 2) after the neonatologist deems that in-room resuscitation is complete and 3) at admission to the Neonatal Intensive Care Unit (NICU), Mother Baby Unit (MBU) or Post-Anesthesia Care Unit (PACU) depending on the baby's needs; determined by the resuscitating physicians. These measurements will be recorded by research nurses in a data collection sheet. Further, the research nurse will record the time from delivery to the time it takes for the infant to arrive at the warmer. Upon arrival at the warmer, the mattress and wrap will be removed as neonatal evaluation takes place.

As immediate neonatal temperature is not generally discussed with patients unless there is an issue such as concern for infection, neonatal temperature will not be routinely discussed with all participants. Only if there is concern for neonatal infection or if there is hyperthermia (>37.5 degrees C) will the study results be discussed with the patient.

Identifiers might be removed and the de-identified information may be used for future research without additional informed consent from the subject.

**E. Chart Review**

All outcomes will be recorded in a REDCap database by research nurses and data managers on the OUHSC campus in prospective fashion. Data will be obtained from maternal and neonatal electronic medical records and only de-identified data will be analyzed from the REDCap database. The primary outcome will be the proportion of hypothermic newborns. Secondary outcomes will include temperature at completion of resuscitation, need for NICU admission, temperature upon leaving the delivery room, temperature upon admission to the NICU (if required), hypoglycemia (less than 30mg/dL in the first 24 hours), highest bilirubin level, maximal respiratory support and duration of respiratory support including but not limited to supplemental oxygen and mechanical ventilation, pulmonary hemorrhage, hyperthermia (>37.5 degrees C), days in the NICU, and composite neonatal morbidity and mortality outcome inclusive of 1) death, 2) intraventricular hemorrhage (all grades), 3) sepsis (determined by treating neonatologist) and 4) Necrotizing enterocolitis. Confounders that will be assessed will include delivery room temperature as reported on the room thermostat, maternal temperature as recorded by anesthesia at the time of delivery, time from delivery to arrival at the neonatal warmer, indication for delivery, indication for cesarean, infant weight, timing of betamethasone administration (time for administration to delivery) and gestational age. Access to the database will be controlled and logged using REDCap's internal systems. Finally, at the completion of the study, the data will be stored for 7 years in order to complete analysis and apply for additional grants prior to being destroyed.

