Recent recommendations from the American Academy of Pediatrics (AAP) and American College of Obstetricians and Gynecologists (ACOG) recommend delayed clamping of the umbilical cord by 30-60 seconds to minimize severe complications such as intraventricular hemorrhage, necrotizing enterocolitis, and anemia in preterm infants. During this period, the infant remains at risk of hypothermia as heat loss starts immediately after delivery. The infant moves from an environment of the 37°C womb to the temperature in the delivery room, with decreases in temperature between 0.2-1 degree every minute. With the above recommended interventions, the neonate typically does not arrive at the radiant warmer for assessment by the neonatology team until 2-3 minutes of life. Prior studies have investigated warming the neonate using transport mattresses and polyethylene wraps after evaluation by the neonatology team and demonstrated efficacy in minimizing hypothermia at admission to the NICU. There are no contemporary studies evaluating strategies to maintain infant euthermia during delayed cord clamping. As such, there remains a critical gap during which hypothermia may develop and adversely affect the neonatal transition to extrauterine life.

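### Admission temperature is listed as an outcome only for NICU infants although it is recorded for every infant, so its natural reading is a comparison in a group formed after randomisation

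*Combined protocol and SAP*

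**What the plan says.** The secondary outcome lists in A. Specific Aims and E. Chart Review both contain "temperature upon admission to the NICU (if required". Neither list names an admission temperature for any other unit.

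The measurement schedule in Section D (Protocol) is wider. Its third temperature recording is made "at admission to the Neonatal Intensive Care Unit (NICU), Mother Baby Unit (MBU) or Post-Anesthesia Care Unit (PACU", according to the baby's "needs; determined by the resuscitating physicians". An admission temperature is therefore planned for every infant.

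Three other statements bear on the point:

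- Randomisation takes place just before surgery, and "neither the patient nor the neonatal team will be blinded to the group assignment" (Section D, Protocol).
- Need for NICU admission is a secondary outcome in its own right (Sections A and E).
- Section J says that primary and secondary outcomes are compared by intent-to-treat. It names no analysis set for individual outcomes and does not say how infants who never enter the NICU are handled for this one.

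**The concern.** If the outcome is analysed as listed, the arms are compared only among infants admitted to the NICU. Membership of that group is decided after randomisation, by physicians who know the assignment, and it could itself be changed by the intervention. Randomisation does not protect such a comparison: the NICU infants in the two arms need not be alike, even if the arms as a whole are.

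Two things are at stake. One is precision, because readings planned in the Mother Baby Unit and the Post-Anesthesia Care Unit would go unused for this outcome. The other is interpretation. Section J says that the pilot is to supply parameters for a full-scale trial, and an effect or SD from a selected group is a poorer planning input than one from all infants. Of the three Section D recordings, admission is the only one made after the infant leaves the delivery room.

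**Working it through.** The plan gives no figure for this outcome, so there is nothing to reproduce. The check sets the texts side by side and then sizes the consequence.

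**Texts.** Outcome lists (Sections A and E): NICU only. Recording (Section D): NICU, MBU or PACU. Order of events: randomisation, delivery, resuscitation, choice of unit. Analysis rule (Section J): intent-to-treat, with no set named. The listed outcome is narrower than the recorded measurement, and the narrowing depends on an event after randomisation.

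**Precision.** Inputs: 74 patients allocated 1:1 (Section A), so 37 per arm if each mother contributes one infant. Assumptions: SD = 1 in NICU infants and in all infants, and the same NICU share f in both arms. The documents give no NICU share, so a range is shown. With n = 37f, the 95% half-width is t(0.975, 2n − 2) × √(2/n).

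| NICU share f | n per arm | Half-width (SD) | Ratio to all infants |
|---|---|---|---|
| 100% (all infants) | 37 | 1.993 × 0.2325 = 0.463 | 1.00 |
| 90% | 33.3 | 1.997 × 0.2451 = 0.49 | 1.06 |
| 80% | 29.6 | 2.002 × 0.2599 = 0.52 | 1.12 |
| 70% | 25.9 | 2.009 × 0.2779 = 0.558 | 1.20 |
| 50% | 18.5 | 2.030 × 0.3288 = 0.667 | 1.44 |
| 40% | 14.8 | 2.050 × 0.3676 = 0.754 | 1.63 |

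The last column is also the break-even for pooling units. If analysing all destinations together raised the SD by 20%, the all-infant half-width would be 0.463 × 1.20 = 0.556, and the gain at a 70% share would be gone. At 50% and 40% the SD would have to rise by 44% and 63%.

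If colder infants are admitted more often, the NICU SD is smaller. At an assumed log-odds of 1.0 per SD it is 0.91 to 0.93, and the half-width becomes 0.558 × 0.93 = 0.52 at a 70% share and 0.754 × 0.91 = 0.69 at 40%.

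**Selection bias.** Assumed model: temperature is N(0, 1) in control and N(d, 1) in intervention, and logit P(NICU) = a − b × temperature + g × arm. The intercept a is set to give a NICU share of 40%, 50% or 70%, and b is 0.5 or 1.0. The bias is the difference among NICU infants minus d, by numerical integration.

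| True effect d (SD) | Arm-specific log-odds g | Bias (SD) | Largest size in standard errors |
|---|---|---|---|
| 0 | 0 | 0 | 0 |
| 0 | ±0.5 | 0.04 to 0.09, either sign | 0.29 |
| 0.66 | 0 | −0.03 to −0.12 | 0.37 |
| 0.66 | ±0.5 | −0.20 to +0.02 | 0.65 |

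The value 0.66 SD is the difference detectable with 80% power at 37 per arm. It is not an expected effect.

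A second model lets unmeasured frailty drive admission, with a frailty–temperature correlation of 0.3 to 0.5 and no true effect. If fewer intervention infants are admitted (for example 50% v 40%, or 70% v 50%), it gives −0.05 to −0.18 SD, always against the intervention. With equal admission it gives no bias. The sign therefore depends on the model.

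**The case against.** The strongest reply is that the restriction is inferred. The words in parentheses may only say when a NICU value exists, the lists say what outcomes will include, and Section J applies intent-to-treat to secondary outcomes without naming a NICU-only set. This stands. A reader might go further and infer that the plan breaks its own intent-to-treat rule, or that its result will be biased. The documents do not support either inference. No text prescribes a NICU-only set, and nothing in the plan fixes the NICU share, how admission depends on temperature, or whether it will differ by arm.

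Other temperatures are listed without a NICU restriction: "temperature at completion of resuscitation, need for NICU admission, temperature upon leaving the delivery room" contains two, and hyperthermia has no stated time point in those lists, so MBU and PACU readings might feed it. This lowers the stakes, but none of these is named as an admission temperature for all infants.

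The NICU share may exceed 70%, since recruitment aims for at least 44 pregnancies below 35 weeks. At 80% to 90% the half-width is 0.52 to 0.49 SD, a small loss. This also stands.

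NICU admission temperature is the endpoint of the earlier work that, in Section B, "demonstrated efficacy in minimizing hypothermia at admission to the NICU". Pooling three destinations mixes settings and measurement times. That is a reason to keep the NICU-only result for comparison, but not to make it the randomised comparison.

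Finally, "Upon arrival at the warmer, the mattress and wrap will be removed as neonatal evaluation takes place". Any effect may have faded by admission, so 0.66 SD is a generous value to assume.

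**Conclusion.** The point holds as a minor one. The lists name admission temperature for NICU infants only, while the schedule records it for all. Followed as listed, the outcome is compared in a group formed after randomisation, by an unblinded team, on the basis of an event that is itself an outcome.

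The precision loss runs from nil if every infant goes to the NICU to a half-width of 0.75 instead of 0.46 SD at an assumed 40% share. It rests on 37 infants per arm, equal SDs and an assumed share. The bias cannot be sized or signed from the documents. In the models tried, with arm-specific log-odds up to 0.5, it stays below one standard error. This is one of many secondary outcomes, no power is claimed for it, and the trial is a pilot. The case for change is that the all-infant comparison uses readings already planned.

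**What to change.** In Sections A and E, define the outcome as temperature at admission to the first receiving unit (NICU, MBU or PACU), compared in all randomised infants by assigned arm. Report the receiving unit and the time from birth to this reading by arm. Keep the NICU-only result, labelled descriptive, for comparison with earlier studies.

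The cost is small: wording in two sections and no new temperature readings. In Section D, "the research nurse will record the time from delivery to the time it takes for the infant to arrive at the warmer", which does not time the admission reading. That time can come from the medical record, which Section E already names as a data source, or from one added entry on the data sheet.

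The downside is that settings and measurement times differ by destination and may raise the SD. Reporting unit and time shows this but does not remove it.

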#### **A. Specific Aims**

We *hypothesize* that neonates delivered preterm and wrapped with a sterile polyethylene wrap while being warmed with a standard neonatal transport warming mattress immediately after birth and awaiting delayed cord clamping will be less likely to be hypothermic at arrival to the neonatal warmer. Since this is not currently a method that is employed, we have insufficient preliminary data to determine a sufficient sample size needed for a randomized controlled trial. **The aim of this grant is to perform a pilot trial investigating the effect size of immediate neonatal warming and wrapping of preterm infants on neonatal temperature.** Our team is well positioned to address these questions as there is tremendous synergy between the maternal fetal medicine and neonatology groups at OU, and our large referral base for preterm deliveries—we accept 600 maternal transfers yearly.

We propose a pragmatic randomized pilot trial evaluating the effect size of this strategy employed for moderate and late preterm infants (32 weeks 0 days to 36 weeks 6 days) who are being delivered by non-emergent cesarean. We plan on enrolling 74 patients and allocating patients to the intervention and control groups 1:1 using a block randomization scheme stratified by gestational age. Patients and clinicians cannot be practically blinded to the interventions given the physical nature of the interventions; however, statisticians will be blinded to the group assignments. Primary outcome will be the difference in temperature of the neonate at time of arrival to the warmer for neonatal evaluation between groups. Secondary outcomes will include temperature at completion of resuscitation, need for NICU admission, temperature upon leaving the delivery room, temperature upon admission to the NICU (if required), hypoglycemia (less than 30mg/dL in the first 24 hours), highest bilirubin level, respiratory support in the form of intubation or continuous positive airway pressure, pulmonary hemorrhage, hyperthermia ( $>37.5$

degrees C), days in the NICU, and composite neonatal morbidity and mortality outcome of death or intraventricular hemorrhage (all grades), sepsis (determined by treating neonatologist). Data obtained from this pilot trial will be used to apply for a NIH K08 grant in order to perform an adequately powered multi-center randomized controlled trial in order to investigate the efficacy of this approach and associated outcomes.

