### Hypothermia and Neonatal outcomes

An important component of care in the first few minutes of life, especially in the preterm neonate is ensuring euthermia. Neonates have decreases in their body temperature of 0.2-1 degrees per minute after birth. Preterm neonates are at increased risk for hypothermia due to their increased body surface to weight ratios, thin skin and lower amounts of insulating subcutaneous fat, thus resulting in increased evaporative heat losses. Hypothermia results in increased metabolic and oxygen demands and impaired resuscitation. From an outcome perspective, hypothermic neonates are at an increased risk for respiratory distress, chronic lung disease, metabolic derangements such as hypoglycemia, intraventricular hemorrhage, and late onset sepsis. Even moderate hypothermia (<36 degrees C) has been linked to mortality. De Almeida et al noted that 44% of preterm neonates admitted to one of 12 university hospitals were hypothermic at 5 minutes of life, with 51% experiencing hypothermia at NICU admission. As such, various interventions have been studied during the golden hour and at the time of neonatal transport to the NICU. These include using polyethylene wraps and caps, warming mattresses, warmed humidified gases and maintaining delivery room temperatures at 24 degrees C. Though such interventions may result in hyperthermia (>37.5 degrees C), no correlation between iatrogenic hyperthermia and adverse neonatal outcomes has been demonstrated. However, strategies to avoid hypothermia reduce the need for respiratory support and lower the risk of pulmonary hemorrhage. Thus, beginning to prevent hypothermia during delayed cord clamping presents itself as an opportunity for improvement in outcomes.

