#### **J. Statistical Methods**

Since this intervention has not been studied previously and requires cohesion between pediatricians and obstetricians, we will plan on hosting in-person and virtual training for key study personnel. Currently, at OU we deliver approximately 250 neonates between 32 and 36 weeks gestation via cesarean each year. Assuming a 33% rate of enrollment, it would take us approximately 11 months to enroll our target sample size of 74 patients.

Two prior studies, one evaluating epidemiology and the other an intervention, demonstrated that 29% of neonates born in the late preterm period were hypothermic in the delivery room with a standard deviation of 8.8. With the proposed enrollment of 74 preterm infants that meet inclusion criteria, we would have approximately 80% power to detect a difference between the two groups of 20%. Since this intervention has not been evaluated previously and we are using indirect data from other institutions and other interventions, we are assuming a 10% increase in sample size (calculated at 68) to account for variations (total of 74). This is a pilot trial to generate the parameters needed to guide the development of the next-step full-scale multicenter trial. Thus, power calculations for the efficacy of the intervention were completed to ensure we did not need to start with a larger or smaller sample size, given the pilot nature of the project.

For this pilot trial, the baseline characteristics of patients assigned to the intervention and control groups will be estimated and compared as means, medians or proportions, as appropriate for the distribution of the data. Descriptive statistics (i.e., proportions, 95% confidence intervals, means, standard deviation, medians, and interquartile range) will be used to characterize the distribution of the primary and secondary outcome measures among the intervention and control groups. Using an intent-to-treat approach, the primary and secondary outcomes will be compared between treatment groups using Student's t-tests, Wilcoxon rank sum tests, chi-square tests or Fisher's exact tests, as appropriate for the variable distributions.

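### Glucose is planned only as a yes/no event below 30 mg/dL; adding the lowest value as a continuous secondary outcome would recover precision at little cost

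*Combined protocol and SAP*

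**What the plan says.** Section A (Specific Aims) and Section E (Chart Review) give the same secondary outcome: "hypoglycemia (less than 30mg/dL in the first 24 hours), highest bilirubin level". Glucose is reduced to an event, while the next item, bilirubin, stays a level. Neither section names a lowest, mean or other continuous glucose measure.

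On the data source, Section E says "Data will be obtained from maternal and neonatal electronic medical records". On size, Section A says "We plan on enrolling 74 patients and allocating patients to the intervention and control groups 1:1", and Section J (Statistical Methods) counts the 74 as infants, so there are 37 per arm. For proportions, Section J offers "chi-square tests or Fisher's exact tests, as appropriate for the variable distributions". It also lists t-tests and Wilcoxon tests for other outcomes, and descriptive summaries with 95% confidence intervals. It states no significance level, no expected rate of hypoglycemia and no detectable difference for this outcome.

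Glucose is part of the rationale. The Abstract names low glucose as a consequence of hypothermia, and the background section on hypothermia and neonatal outcomes lists "metabolic derangements such as hypoglycemia" among the harms.

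**The concern.** Glucose is one of the pathways by which the plan expects hypothermia to do harm. Recording only whether it fell below a threshold discards how low each tested infant went. With 37 infants per arm, a binary outcome that may be uncommon has low power and gives an imprecise rate.

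Section J says the pilot is meant to supply parameters for a larger trial. As defined, the outcome would give that trial an event proportion, but no planned estimate of a glucose mean or SD. A numeric value must exist for each infant whose event status is scored from a test, so the extra information comes almost free.

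**Working it through.** **Inputs**
- From the plan: 37 infants per arm (74 randomised 1:1); binary outcome at 30 mg/dL; chi-square or Fisher's exact test.
- Assumed: two-sided 5%, in line with the 95% intervals in Section J; Fisher's test, because expected counts are small; true control rates of 5% to 20%; shifts of 0.4 and 0.66 SD in lowest glucose. The plan gives no glucose SD, so shifts cannot be converted to mg/dL.

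The plan states no power or detectable difference for hypoglycemia, so there is no figure of its own to reproduce.

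**Step 1: smallest significant result with no treated events.** With equal arms and all k events among controls, the two-sided Fisher p-value is 2 × C(37,k) / C(74,k).

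| Control vs treated | Observed control rate | Fisher p |
|---|---|---|
| 4 vs 0 | 10.8% | 0.115 |
| 5 vs 0 | 13.5% | 0.054 |
| 6 vs 0 | 16.2% | 0.025 |

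For k = 6: 2 × 2,324,784 / 185,250,786 = 0.025. The Yates-corrected chi-square has the same threshold (5 vs 0: 0.064; 6 vs 0: 0.033). The uncorrected chi-square crosses 5% at 4 vs 0 (p = 0.040), but the expected count there is only 2 events per arm.

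**Step 2: power if every case is eliminated.** The treated count is then always 0, so power is the probability of at least 6 control events, P(X ≥ 6) with X ~ Binomial(37, p).

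| True control rate | Fisher power |
|---|---|
| 5% | 1% |
| 10% | 16% |
| 15% | 49% |
| 20% | 78% |

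**Step 3: information kept by the count.** Under a normal model, the large-sample efficiency of the count relative to the continuous value is φ(z)² / [p(1−p)], with z = Φ⁻¹(p).
- p = 5%: 0.1031² / 0.0475 = 0.22, equivalent to about 8 of 37 infants per arm.
- p = 10%: 0.1755² / 0.09 = 0.34, about 13 per arm.
- p = 15%: 0.2332² / 0.1275 = 0.43, about 16 per arm.

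**Step 4: power for the same shift, analysed both ways.** For an upward shift of d SD, the treated rate is Φ(Φ⁻¹(p) − d). Fisher power is summed exactly over the two binomials. For the continuous value, power comes from the noncentral t distribution with noncentrality d × √(n/2): 0.4 × √18.5 = 1.72 and 0.66 × √18.5 = 2.84.

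| Shift | t-test, 37 tested per arm | Fisher at control rate 5% | 10% | 15% |
|---|---|---|---|---|
| 0.4 SD | 40% | 0.5% | 4% | 8% |
| 0.66 SD | 80% | 1% | 7% | 17% |

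If only 25 infants per arm were tested, t-test power for 0.66 SD would fall to 63%.

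**The case against.** The strongest objection concerns who is tested. The plan does not say that every infant has a glucose measurement, or when or how often. A minimum tends to fall with more tests, and the neonatal team is not blinded, so selective testing could bias a comparison of lowest values. This stands as a limitation. The yes/no event shares it, since an untested infant cannot be scored and more tests give more chances to cross the threshold.

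The effect sizes are also assumed. A shift of 0.66 SD is simply what gives 80% power with 37 per arm, and nothing in the plan supports a shift that large after 2 to 3 minutes of exposure. This stands too: at 0.2 SD the t-test has only 14% power. The continuous form is more efficient at any shift under the normal model, but at modest shifts either analysis would usually be non-significant.

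Finally, this is a secondary outcome in a pilot. A threshold event is a legitimate choice, and its proportion with a confidence interval is a usable planning parameter. That limits the weight of the point but does not argue against an inexpensive addition.

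Some stronger readings are tempting but unsupported:
- **That no benefit can be detected unless 16% of controls are truly affected.** The 16% is an observed threshold under Fisher's test, not a true rate.
- **That the pilot must report no difference whatever the truth.** With complete elimination, power is 78% at a true control rate of 20%.
- **That the count carries almost no information.** It keeps roughly a fifth to two fifths over the assumed range.
- **That raw glucose values will not be captured.** The REDCap form is not shown; the documents show only that no continuous glucose outcome is planned.

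**Conclusion.** The point holds as a minor improvement. The plan names glucose only as an event below 30 mg/dL, and that form uses an estimated 22% to 43% of the information in the lowest value at control rates of 5% to 15%. For a 0.4 SD shift this means about 40% power against 0.5% to 8%; for 0.66 SD, about 80% against 1% to 17%.

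These figures rest on a two-sided 5% level, Fisher's test, a normal model, assumed control rates and shifts, and all 37 infants per arm being tested. The direction of the comparison does not depend on the particular shift chosen; its size does. The cost is lost precision in one secondary outcome. The primary inference is not affected.

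**What to change.** In Sections A and E, add lowest glucose (mg/dL) in the first 24 hours as a continuous secondary outcome among infants tested. In Section J, specify a between-arm difference with a 95% confidence interval, using a rank-based method if the values are skewed. Keep the proportion below 30 mg/dL with its confidence interval, and name the test to be used for it. Report by arm the number of infants tested and the number of tests per infant, so that readers can judge whether the lowest values are comparable.

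The cost is one numeric REDCap field for the value, a record of the number of tests, and one more secondary analysis. It needs no additional glucose tests or patients, although the precision gained depends on how many infants are tested in routine care. The lowest value will still depend on who is tested and how often, and the report should say so.
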